4.0 Study Interventions/Investigational Agent(s)

Description: LB is a long acting local anesthetic. It is liposome encapsulated bupivacaine which allows for prolonged release of bupivacaine over a 72-hour period. Bupivacaine is a medium acting local anesthetic which provides between 6 and 24 hours of analgesia when used in a peripheral nerve block. Both medications are standard of care for use in interscalene blocks here at the U of MN. Acetaminophen is a medication used to treat pain, gabapentin is a gabapentinoid which is used to treat postoperative pain, and Celebrex is a selective COX-2 inhibitor also used to treat pain.

Drug/Device Handling: The LB will be stored in a locked pyxis fridge in a box labeled Liposomal Bupivacaine. The anesthesiologists in charge of regional anesthesia the day the procedure will be informed will write the order for dispensing the medication and the block per standard of care. It will be retrieved by the PI and sub I's for use in the interscalene blocks.

Biosafety: Per standard of care

Stem Cells: N/A

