5.0 Procedures Involved

Study Design: Level I randomized prospective outcomes study comparing two groups of patients. Patients will be assigned either to Liposomal Bupivacaine plus bupivacaine for an interscalene block or they will receive bupivacaine for an interscalene block injection.

Study Procedures: After consenting to the study (either in clinic or the PAC clinic) and completion of the preoperative process (per standard of care), a randomization scheme from a random number generator will be followed to ensure equal likelihood of group assignment. The patient will be placed in the supine position with the head of the bed elevated 30 degrees with standard ASA monitors applied. Sedation will be provided with midazolam 0-2mg and propofol 0-50 mg. The interscalene groove will be identified with the ultrasound. Using sterile technique, a 21g Nerve block needle will then be inserted and advanced under ultrasound guidance until it is in the interscalene groove. Once in the interscalene groove, 20 mL of local anesthetic will be injected, with 10mL deposited at the top of the brachial plexus and 10mL at the bottom. In the study group, 5 mL of each 0.5% bupivacaine and LB will be injected at each location.

PROTOCOL TITLE: Prospective Randomized controlled trial comparing liposomal bupivacaine to bupivacaine Interscalene blocks for total shoulder arthroplasty surgery

VERSION DATE: 7/6/2020

The control group will have 20mL of 0.5% bupivacaine divided between the injection sites. Patients would be required to take a dose of acetaminophen 975 mg oral, gabapentin 300 mg oral, and Celebrex 400 mg oral prior to surgery (per standard of care). The patient will be monitored (vital signs, respiratory status and oxygen saturation) in the preoperative area until he/she is brought into the operating room for their procedure. A working block prior to surgery will be confirmed via sensory testing of the shoulder.

All patients will undergo a standard induction with propofol 1.5-3.0 mg/kg, lidocaine 60-100 mg, ondansetron 4 mg, dexamethasone 10 mg and ketamine 0.25 mg/kg. An LMA or ETT will be placed and an opioid sparing technique will occur. Standardized maintenance will be a propofol infusion without neuromuscular blockers. 25-50 mcg of IV Fentanyl will be utilized for increases in heart rate greater than 20% or increases in systolic blood pressure above baseline.

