An analysis of the total cost of analgesics will be tabulated at the conclusion of the study to determine the most cost effective treatment option as this will be

PROTOCOL TITLE: Prospective Randomized controlled trial comparing liposomal bupivacaine to bupivacaine Interscalene blocks for total shoulder arthroplasty surgery

VERSION DATE: 7/6/2020

added into the cost of hospitalization including the number of days each patient spent in the hospital.

Blinding Procedure: A random number generator will be used to determine if the patient will have LB plus bupivacaine or bupivacaine for their interscalene block. The primary investigator will access the number generator in the pre-op area immediately prior to block placement. The website www.random.org will be used as the random number generator.

The research assistant in this study will be blinded to the method of analgesia for the patient. This person will not be responsible for any clinical testing and will record all data in the protected database daily. They will not have any access to the patients' clinical records or chart. **Any questions from the patient will be referred to the on-call resident or staff on call.**

Study Duration: We anticipate the study to take approximately 1 year from the date of enrollment of the first patient. Patients will be in the study for 14 days and then their chart monitored for up to 30 days post surgery. The data analysis should take one month after full enrollment of the study.

Individually Identifiable Health Information: This study involves the use of individually identifiable health information. Please see attached HIPAA authorization form.

Use of Radiation: N/A

Use of Center for Magnetic Resonance Research: N/A

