12.0 Withdrawal of Participants

Withdrawal Circumstances: Subjects who have consented prior to the day of surgery and for some reason choose not to participate will be withdrawn and a notation will be made in the study records and these people will be considered screen failures. The surgeon may choose to withdraw the patient from the study prior to surgery for any medical reason or if they suffer a major life threatening adverse event.

Withdrawal Procedures: If the patient is withdrawn from study prior to the procedure, they will be noted in study records as screen failures. If they undergo the procedure and they decide they no longer want to be a part of the study or withdrawn by the physician, they will be withdrawn and no further data will be collected. This will also be noted in the study documentation.

Termination Procedures: If the study is terminated for any reason, or there is more than 5 % major adverse events the data that is already collected will be stored in a secure location only accessible to research personnel on this study. No further data will be collected if the study is terminated.

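### The investigator draws each arm on a public website with no described record of draws, and the screen-failure rule does not stop at the draw, so first allocations cannot be fully verified

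*Combined protocol and SAP*

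**What the plan says.** **Allocation.** Section 5.0 (Study Procedures) says that after consent and the preoperative work-up, "a randomization scheme from a random number generator will be followed to ensure equal likelihood of group assignment". The Blinding Procedure paragraph of the same section gives the mechanism: "The primary investigator will access the number generator in the pre-op area immediately prior to block placement", and "The website www.random.org will be used as the random number generator". No section describes a stored list, a custodian, sealed envelopes, a saved draw or a randomisation log.

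**Who is involved.** Under section 4.0 the investigator and sub-investigators fetch the liposomal bupivacaine (LB) for the blocks, and the regional anaesthesiologists on duty "will write the order for dispensing the medication and the block per standard of care". Section 5.0 describes only the research staff who collect outcomes as blinded. The Study Summary calls the trial double blind without saying who is masked.

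**Withdrawal.** Section 12.0 states: "If the patient is withdrawn from study prior to the procedure, they will be noted in study records as screen failures". It also states: "The surgeon may choose to withdraw the patient from the study prior to surgery for any medical reason". Neither sentence mentions the draw, and section 12.0 does not define the procedure.

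**Order of events.** Section 5.0 places the block in the preoperative area. The patient is then monitored "in the preoperative area until he/she is brought into the operating room for their procedure", and "A working block prior to surgery will be confirmed via sensory testing of the shoulder".

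**Analysis.** Section 15.0 gives 70 patients, 35 per group: 30 from a pilot and 40 additional. It defines no analysis set and no accounting of patients by arm.

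**The concern.** The 72-hour opioid comparison is protected by randomisation only if each patient is analysed in the first arm drawn and everyone drawn is accounted for by arm. The plan leaves two gaps.

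1. The person who draws the arm is on the treating team and works alone on a website. If a draw were repeated or set aside, no described record would show it.
2. A patient can leave the study after the draw and be filed with people who were never randomised. The surgeon may trigger this before surgery, and no section says whether the surgeon knows the arm.

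If either happened selectively by prognosis, the groups would differ for a reason other than treatment. For a discarded draw, or a withdrawal between draw and drug order, the described records would not reveal it.

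**Working it through.** **Step 1: how long the window in section 12.0 is.** Section 5.0 gives the order as consent, draw, block, sensory test, operating room.

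- If the procedure means the block, the window after the draw is short, because the draw comes immediately before the block.
- If it means the operation, which is how section 5.0 uses the word when the patient is taken to the operating room, the window runs from the draw through the block and its sensory test. It then includes patients already treated.

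On both readings the window opens at the draw.

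**Step 2: what existing records can recover.**

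| Situation | Drug order and Epic show | Not shown |
|---|---|---|
| Patient treated and analysed | Treatment given | Whether it was the first draw |
| Withdrawn after the block | Treatment given | Whether it was the first draw; no requirement to report by arm |
| Withdrawn between draw and order | Nothing on arm | The arm drawn |
| Draw repeated or discarded | Nothing | That it happened |

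**Step 3: whether arm counts would expose it.** If all 70 were independent 50:50 draws, a split of 40:30 or worse has probability 28%. Unequal counts would therefore not be informative.

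**Step 4: illustrative size.** The documents give 70 patients, 35 per arm, and 40 after the pilot. They give no alpha, effect size or SD, so the 80% power figure cannot be reproduced. It is not needed here. My assumptions are:

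- no true effect, a normal outcome, and a two-sided 5% t-test;
- the 30 pilot patients unaffected and split 15/15;
- a prognosis score correlated r = 0.3 to 0.5 with opioid use;
- all interference in one direction.

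*Overturned draws.* Each one moves a patient with mean absolute score √(2/π) = 0.798 from one arm to the other, so for k overturned draws

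bias = k × 2 × 0.798 × r / 35.

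- k = 1: 2 × 0.798 × 0.3 / 35 = 0.014 SD; with r = 0.5, 0.023 SD.
- k = 4: 0.055 SD; with r = 0.5, 0.091 SD.

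The standard error is √(2/35) = 0.239 SD. The false-positive rate is about Φ(−1.96 + bias/0.239) + Φ(−1.96 − bias/0.239).

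- k = 4, r = 0.3: bias/0.239 = 0.229, giving 0.0417 + 0.0143 = 5.6%.
- k = 4, r = 0.5: bias/0.239 = 0.381, giving 0.0572 + 0.0096 = 6.7%.

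Simulation (200,000 trials per setting) gives 5.7% and 6.7% for k = 4, and 5.0 to 5.1% for k = 1. Four overturned draws correspond to steering 8 of the 40 patients (20%), since half would have drawn the wanted arm anyway.

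*Selective withdrawal after an LB draw.* If k poorer-prognosis patients leave and are replaced, 40 + k draws are made. LB then retains 15 + (40 + k)/2 − k = 35 − k/2 patients, and

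bias ≈ k × 0.798 × r / (35 − k/2).

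For k = 4 this is 4 × 0.798 × 0.3 / 33 = 0.029 SD, or 0.048 SD with r = 0.5. Simulation gives 0.029 to 0.049 SD and 5.2 to 5.6% false positives. One withdrawal gives about 0.01 SD and 5.1%. Eight, an extreme case, give 0.06 to 0.10 SD and 5.8 to 7.3%.

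**The case against.** Much can be said for the plan, and most of it stands.

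- *Allocation is concealed at enrolment.* Consent comes first and independent draws cannot be predicted. That is right. A reader might infer that the investigator can foresee the next arm, and nothing in the documents supports this.
- *The protocol never says that a patient is a screen failure after the draw.* Correct. A reader might take it as stated. It follows only from the absence of a cut-off and from an undefined word, and on the block reading the window is brief.
- *Treatment can be traced.* Orders and Epic would show it for any patient whose drug was ordered, and withdrawals are noted in study records. A reader might infer that the arms of all withdrawn patients are lost. The loss is limited to the first draw and to withdrawals between draw and order.
- *The scheme to be followed could be a prepared list.* Possible, but the Blinding Procedure paragraph sends the investigator to the generator for each patient, and no list is described.
- *The trial is called double blind.* That bears on the surgeon's withdrawals but does not say whether the surgeon is masked.
- *The numbers are weak support.* They are. One event is negligible, and the larger figures need consistent steering. Dropping the patients with the very highest outcomes would give larger error rates, but nobody could identify them before surgery. How the pilot was allocated and how many draws remain after dropout are also not documented.

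What is left is narrower: no record of first draws, and no rule that keeps every drawn patient in the accounts by arm.

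**Conclusion.** The point holds as a weakness in allocation records and patient accounting that should be corrected. It is not evidence that any draw was repeated or any patient removed selectively, and the documents do not support such an inference. The main loss is that correct allocation could not be demonstrated if questioned.

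The likely bias is small: negligible for one event, and about 0.05 to 0.09 SD with 5.7 to 6.7% false positives for four overturned draws among 40. These sizes rest on the assumptions listed in the working, none of which comes from the documents. The textual part does not depend on them. How far the screen-failure rule reaches depends on what the procedure means, and the protocol has to settle that.

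**What to change.** For all patients still to be randomised:

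1. **Allocation (section 5.0).** Replace the website sentences in the Blinding Procedure paragraph, and align the Study Procedures text, with wording such as: *A staff member who takes no part in enrolment or block placement holds a pre-generated 1:1 sequence and, just before the block, releases one locked, time-stamped assignment for each consented, eligible patient.* If the analyst is to be masked, this person should also be outside the analysis. Use REDCap randomisation if available. Section 20.0 shows REDCap only for e-consent, so availability is an assumption. Otherwise use sequentially numbered, opaque, sealed envelopes kept by the custodian and not by the investigator, because envelopes within reach could be opened early.
2. **Log.** Record every release by study identifier, arm, date and time, including patients later withdrawn.
3. **Withdrawal (section 12.0).** End screen failure at release of the assignment. State that a patient withdrawn after release counts as randomised, is reported by assigned arm with the reason, and is included in the primary analysis by assigned arm wherever outcome data exist.

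The cost is a small one-off set-up and a wording change. It needs no extra patients and changes no clinical management: the surgeon's discretion to withdraw a patient is unaffected, and only the accounting changes.

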6.0 Data and Specimen Banking

Storage and Access: All study data will be stored on excel spreadsheets stored in Box. Only the PI and members of the research team will have access to the data.

Data: The data from this study will be collected both from Epic and directly from the patient. The data collected includes: demographic data, age, weight, ASA class, duration of surgery, length of stay in recovery room both phase 1 and 2, length of hospital stay, amount of opioids given intraoperatively and post-operatively, non-opioid pain medication, pain score (0-10) at 2, 6, 24, 48, and 72 hours, satisfaction with treatment, Quality of Recovery survey at 72 hours and 14 days, and any adverse events.

Release/Sharing: N/A

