3.0 Study Endpoints/Events/Outcomes

Primary Endpoint/Event/Outcome: To determine if LB plus bupivacaine in an interscalene block results in less opioid use over 72 hours compared to bupivacaine only for TSA surgery.

Secondary Endpoint(s)/Event(s)/Outcome(s):

- To determine if LB plus bupivacaine in an interscalene block results in less pain over 72 hours as compared to bupivacaine only in an interscalene block for TSA surgery. Assessed via total pain scores (Use of Visual Analog Scale)
- To determine if LB plus bupivacaine in an interscalene block results in improved (Quality of Recovery) QOR at 72 hours and 14 days as compared to bupivacaine only in an interscalene block for TSA surgery. Assessed via QOR 15 patient survey.
- To determine if LB plus bupivacaine in an interscalene block results in fewer phone calls to the surgeon within 72 hours as compared to bupivacaine only in an interscalene block for TSA surgery.

PROTOCOL TITLE: Prospective Randomized controlled trial comparing liposomal bupivacaine to bupivacaine Interscalene blocks for total shoulder arthroplasty surgery

VERSION DATE: 7/6/2020

- To determine if LB plus bupivacaine in an interscalene block hastens readiness for hospital discharge compared to bupivacaine only in an interscalene block for TSA surgery.

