While in the hospital all patients will receive a standardized multimodal pain medication regimen. Acetaminophen 975 mg q6 hours, ibuprofen 600mg q6 hours and prn oxycodone 5-10 mg q4 hours or 2-4 mg hydromorphone oral every 4 hours. All patients will be discharged with 30-40 pills of 5 mg oxycodone or 30-40 pills of hydromorphone 2 mg with instructions to take 5-10 mg oxycodone for severe pain every 4 hours as needed or 2-4 mg every 4 hours hydromorphone as needed for severe pain. Patients will be instructed to start with the lower dose, but can repeat the dose if needed up to 10mg oxycodone or 4mg hydromorphone every 4 hours if needed.

Assessments: Post-operatively patients will be evaluated at 2 and 6 hours post-operatively by a blinded research staff. This person will not be aware of the patient's mode of analgesia. The patients will be contacted via in person assessment or via telephone at 24, 48, and 72 hours +/- 5 hours. Patients will be asked to rate their pain on scale of 0-10. The amount of opioids used by the patient will be recorded by study personnel as will any other adjuvant pain medication used. The time in phase 1 and phase 2 of PACU will be recorded. The patients will be asked at 72 hours post-injection if they would undergo an interscalene block with their medication again or if they would choose a different form of pain management (ex: higher doses of pain medications). Patients will fill out a Quality of Recovery Survey at 72 hours and 14 days, and be assessed for block related complications at this time. As part of the research, patients also will undergo diagnostic ultrasound of their diaphragm on POD 1. All complications will be recorded including:

- Failure of the block
- Wound infections
- Subsequent procedures
- Complications related to placement of the interscalene block including nerve injury, prolonged sensory loss greater than three days, prolonged arm weakness greater than three days
- Opioid related side effects of nausea and/or vomiting
- Local anesthetic toxicity as evidenced by seizures or cardiovascular collapse without other reasonable etiology

All data will be recorded on the Clinical Diagnostic Sheet and will then be given to the research coordinator for manual data entry. Data collection will continue until POD #14. At that time study participation will be terminated. Should patients be re-admitted to the hospital in the next two weeks (Up to POD 30) for pain, a notation will be made in study records.

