8.0 Study Population

Inclusion Criteria: All adult patients aged greater than 18 years of age that are undergoing total or reverse total shoulder arthroplasty

Exclusion Criteria: Patients with allergy to local anesthetics, daily use of opioids for more than 3 weeks prior to surgery, patient refusal and those who have opted out of research, patients with coagulopathy, non-english speaking patients, and those who do not have access to a telephone.

Screening: Patients will be screened at their preoperative visit either in the surgeon's office, pre assessment center, or preoperative area.

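### No preoperative pain score or QoR-15 is scheduled, so two secondary comparisons stay unbiased but cannot be baseline-adjusted and may be less precise than they could be

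*Combined protocol and SAP*

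**What the plan says.** Section 3.0 makes pain over 72 hours a secondary endpoint ("Assessed via total pain scores (Use of Visual Analog Scale"). It also asks whether the liposomal arm "results in improved (Quality of Recovery) QOR at 72 hours and 14 days" relative to bupivacaine alone ("Assessed via QOR 15 patient survey").

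The measurement schedule is consistent across sections and entirely postoperative:

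- Section 5.0, Assessments, starts the follow-up: "Post-operatively patients will be evaluated at 2 and 6 hours post-operatively by a blinded research staff". Contacts at 24, 48 and 72 hours come next.
- The same section says "Patients will fill out a Quality of Recovery Survey at 72 hours and 14 days".
- Section 6.0 lists "pain score (0-10) at 2, 6, 24, 48, and 72 hours, satisfaction with treatment, Quality of Recovery survey at 72 hours and 14 days". Its pre-treatment items are demographics, age, weight and ASA class. The list is worded as open-ended, but no other section adds a preoperative pain or QoR value.

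A preoperative contact exists for every patient. Section 8.0 says "Patients will be screened at their preoperative visit", which may be in the surgeon's office, the pre-assessment center or the preoperative area. Section 5.0, Blinding Procedure, has the allocation drawn just before the block is placed. Section 15.0 names no efficacy model and no covariates.

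**The concern.** Where a score taken before treatment correlates with the same score taken afterwards, adjusting for it removes part of the between-patient variation from the error term and narrows the confidence interval for the treatment difference. Without that score, the variation stays in.

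The trial is small, with 35 per arm, and eligibility in section 8.0 does not restrict preoperative pain apart from excluding patients with more than 3 weeks of daily opioid use. A chance difference between arms in preoperative pain or general state could be neither described nor adjusted for directly. A preoperative score cannot be obtained after the block and surgery, so the opportunity is lost patient by patient as enrolment proceeds.

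At stake is the precision of two secondary comparisons.

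**Working it through.** **The plan's own figures.** Section 15.0 gives 70 patients (35 per group) for 80% power, but no endpoint, effect, SD, alpha or sidedness, so the 70 cannot be reproduced. Inverting it under an assumed two-sided alpha of 0.05: (1.960 + 0.842) × √(2/35) = 2.802 × 0.239 = 0.67 SD. Section 10.0's 90 patients fit 20% dropout: 70/0.8 = 87.5, rounded up to 88, and 90 × 0.8 = 72.

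**Chance imbalance.** The standard error of a baseline difference with 35 per arm is √(2/35) = 0.24 SD. A gap above 0.3 SD in either direction has probability 2 × [1 − Φ(0.3/0.239)] = 0.21.

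**Gain from adjustment.** Let r be the correlation between the preoperative score and the follow-up score. It is not in the documents, so 0.1 to 0.6 is assumed.

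- Variance ratio with the covariate: 1 − r². Standard-error ratio: √(1 − r²).
- Equivalent unadjusted N if all 70 have a baseline: 70/(1 − r²).
- Section 15.0 says that 40 patients are added after a 30-patient pilot to total 70. If those 30 are part of the 70 and have no baseline, the equivalent N is about 30 + 40/(1 − r²). This weights the two groups by their own precision; a model with one common residual variance would gain slightly less.
- Power at a true effect of 0.67 SD, all 70 with a baseline: Φ(2.802/√(1 − r²) − 1.960).

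| r | Variance ratio | SE ratio | Equivalent N, all 70 | Equivalent N, 40 of 70 | Power, all 70 |
|---|---|---|---|---|---|
| 0.1 | 0.99 | 0.995 | 70.7 | 70.4 | 80.4% |
| 0.2 | 0.96 | 0.980 | 72.9 | 71.7 | 81.6% |
| 0.3 | 0.91 | 0.954 | 76.9 | 74.0 | 83.6% |
| 0.4 | 0.84 | 0.917 | 83.3 | 77.6 | 86.4% |
| 0.5 | 0.75 | 0.866 | 93.3 | 83.3 | 89.9% |
| 0.6 | 0.64 | 0.800 | 109.4 | 92.5 | 93.8% |

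On the pilot reading, the standard-error ratio is √(70/70.4) = 0.997 at r = 0.1 and √(70/92.5) = 0.870 at r = 0.6. The standard error then falls by at most about 13%, against 20% if everyone has a baseline.

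These figures are for a single follow-up score. For a total pain score the same formula applies, with r the correlation between the preoperative score and that total.

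**The case against.** Much of the opposing case stands.

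- **The correlation is unknown and may be low.** At r of 0.2 or less the gain is negligible: at most 3 patients' worth. Low values are plausible for pain at 2 and 6 hours, when a block confirmed by sensory testing is acting and opioids are given according to pain score.
- **The pilot may cap the gain.** If the 30 pilot patients count toward the 70, up to 43% (30/70) of baselines are already unobtainable.
- **Baseline timing would vary.** Some patients consent in clinic and others on the day of surgery. A varying interval before surgery may weaken r.
- **The postoperative pain measure is itself unsettled.** Section 5.0 asks for maximum pain before discharge, current pain at home and, under Assessments, a 0-10 rating. A covariate does not cure this, nor does it supply the missing efficacy model.

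A reader might infer that, without a baseline, the QoR result at 14 days cannot be interpreted or the comparison is biased. The documents do not support that. The section 3.0 objective compares randomized arms, not change from baseline, and the unadjusted comparison is unbiased. The standard error already allows for chance imbalance. A reader might also suppose that preoperative state carries through strongly to day 14. Nothing in the documents says so, and no pain score is scheduled at day 14.

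What the objection does not remove is that the schedule omits both values, that a contact before allocation already exists, and that collecting them there costs little.

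**Conclusion.** The omission is real, and it is a matter of efficiency, not validity. Two secondary endpoints, pain over 72 hours and QoR-15 at 72 hours and 14 days, cannot be baseline-adjusted as planned. Their between-arm comparisons remain unbiased but may be less precise than they could be. No benefit to the primary endpoint, opioid use over 72 hours, is shown.

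For assumed r of 0.1 to 0.6, the variance of a single score would fall by 1% to 36%. The equivalent N is about 71 to 109 if all 70 patients have a baseline, and about 70 to 93 if the 30 pilot patients are among the 70 and have none. The gain becomes useful from about r = 0.4 and is likely smallest for pain at 2 to 6 hours. The power figures also assume a two-sided alpha of 0.05 and a true effect of 0.67 SD. This is a cheap improvement worth making; the trial's main conclusion does not depend on it.

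**What to change.** In sections 5.0 and 6.0, for all patients still to be enrolled, add one QoR-15 and one 0-10 shoulder pain score, completed after consent and before sedation and allocation. Because allocation is drawn immediately before the block, these would be true pre-randomization covariates.

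In section 15.0, prespecify that QoR-15 at 72 hours and 14 days and the postoperative 0-10 pain scores are compared by ANCOVA, or by a repeated-measures model, with the preoperative score of the same instrument as covariate. State how patients without a baseline value are kept in the analysis, and whether the 30 pilot patients are part of the 70. State also which postoperative pain rating (maximum or current) is analysed, so that the preoperative question can match it.

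The cost is a few minutes per patient at a contact that already takes place, one extra form and a short addition to section 15.0. The drawbacks are a varying interval between form and surgery and some missing baselines: up to 30 of 70 if the pilot patients are counted, plus any lost among patients consented on the day of surgery.
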